### 2.2 Primary Endpoints

Efficacy: visualization of membranes stained based on binary subjective evaluation.

Assessment of efficacy (success) is provided in section 3, Study Endpoints. |

### 2.3 Secondary Endpoints

- Efficacy: subjective assessment of surgical help provided by the product
- Safety:
  - Rate and severity of potential study-related products adverse events
  - Visual outcome at the last postoperative visit

The study hypothesis to be verified is non-inferiority in term of efficacy between study products and comparator based on a binary subjective evaluation of visualization of membranes stained. The proportion of success between study products and comparator will be studied, covariates (age, gender, visual acuity in the affected eye, surgery type being vitrectomy or phaco plus vitrectomy) taken into using a propensity score methodology.

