## 2 Study Objectives and Design

### 2.1 Study objectives

To determine efficacy and safety of MONOBLUE DUAL View and MONOBLUE ILM View (study products) vital stains during vitrectomy surgery

Both study products are CE-marked and legally marketed in Europe. The data collection will serve as Post-Marketing Clinical Follow-up according MDR provisions. Retrospective data will also be collected for the two reference products: ILM Blue® (DORC) and Membrane Blue Dual® (DORC) to serve as control. For this purpose, patient data will be used that were collected in studies S61408 (Comparative study 23G vs 27G vitrectomy), S63610 (Comparative study 27G vitrectomy vs larger gauge surgery) and S64913 (EVA Nexus Field Observation Study).

The expected effect of the study products is to provide the retinal surgeon with adequate aid in visualizing the membranes involved in the retinal pathology to treat, thanks to their staining capabilities. The performance of the study products is related to the visualization of retinal tissues (ILM and/or ERM) during the vitrectomy procedure, when these tissues cannot be distinguished accurately enough without staining. Their use allows for better identification of these tissues and facilitates their removal by the surgeon. The clinical benefit of using ophthalmic dyes is to increase the patient's ability to recover anatomically and functionally by allowing more precise surgery with an effective visualization tool.

Along with collecting post-marketing clinical follow-up data on the subject products, the outcomes of the present study results may be used at the UZLeuven Hospital to decide to use Monoblue ILM View and/or Monoblue Dual View as standard-of-care, replacing Membrane Blue Dual and ILM Blue.

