## 4 Statistics and Data Analysis

The primary outcome of the study is the success of the products based on assessment of efficacy of the staining dye.

Safety of the dye will be assessed by comparing the surgical outcome of the patients to a similar control group that underwent surgery using the staining dyes presently used in our department (see study endpoints).

Statistical analyses will be performed with R version 3.6.2 or higher. In case of missing values, the underlying missingness process (MCAR, MAR or MNAR) will be investigated and 15 multiple imputations will be performed using the **MICE** R package.

We will test with the statistical test of Jamshidian and Jalal (2010), implemented in the **MissMech** R Package (Jamshidian, Jalal & Jansen, 2014), whether missing data were MCAR. If they were not MCAR, we investigated whether or not the missing mechanism could be explained by baseline characteristics (eg, sociodemographic, medical features) of patients using logistic regression, which would suggest an MAR mechanism. If missing data were not MCAR or MAR, they were considered as MNAR.

For each dataset created, two propensity scores will be performed: a first one between the Monoblue ILM View and the ILM Blue, and a second one between the Monoblue Dual View and Membrane Blue Dual. The next covariates were selected for the propensity score: age, gender, visual acuity of the affected eye, surgery type of the affected eye (vitrectomy only vs phaco and vitrectomy). The Covariate Balancing Propensity Score provided in the R **CBPS** package (Imai & Ratkovic, 2014) will be used to estimate an Average Treatment Effect (ATE). The ATE will be estimated by covariate balancing and requesting an exact match. An absolute standardized difference less than 10–15% will be considered to support the assumption of balance between the groups. Unlike the P-value, this method is not affected by the sample size, and it could be used to compare the relative balance of variables that were measured in different units (Austin, 2011). Results (obtained after matching) will be expressed as the mean and standard deviation (SD) for continuous variables or the percentage for categorical variables. The **survey** R package will be used to perform linear regressions for continuous outcome variables and logistic regressions for binary variable. These regressions

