will include the treatment group effect, the weight resulting from the matching, and variables present in the propensity score. This procedure will provide a doubly-robust estimator, which corrected the last remaining possible imbalance between the covariates and produced an unbiased treatment effect (Funk et al., 2010). We will then combine results of the 15 regressions by taking the mean of the estimates of the regression coefficients of the treatment effect and the its associated p-value for each imputed dataset (the so-called, 'Mite approach'), as described by Leyrat et al. (2019). Adjusted P-values less than 0.05 will be considered significant.

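### Section 2.3 sets a non-inferiority hypothesis, but section 4 offers only p<0.05 on a logistic coefficient, with no margin or confidence bound, so similar success rates cannot be declared non-inferior

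*Combined protocol and SAP*

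**What the plan says.** The primary endpoint (section 2.2) is binary: "Efficacy: visualization of membranes stained based on binary subjective evaluation". The hypothesis attached to it appears at the end of section 2.3: "The study hypothesis to be verified is non-inferiority in term of efficacy between study products and comparator". The same paragraph names the quantity of interest: "The proportion of success between study products and comparator will be studied".

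Section 4 does not mention non-inferiority. It provides for two separate comparisons ("For each dataset created, two propensity scores will be performed", one per dye pair) and uses the survey package to "perform linear regressions for continuous outcome variables and logistic regressions for binary variable". Results from the 15 imputed datasets are combined by "taking the mean of the estimates of the regression coefficients of the treatment effect and the its associated p-value for each imputed dataset". The only decision rule is: "Adjusted P-values less than 0.05 will be considered significant". Descriptive results are to be given as mean and SD or as percentages. The null value, the sidedness and the meaning of adjusted are not stated.

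Section 2.1 says the results may be used at the hospital "to decide to use Monoblue ILM View and/or Monoblue Dual View as standard-of-care, replacing Membrane Blue Dual and ILM Blue".

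**The concern.** A non-inferiority claim needs a stated largest acceptable deficit and a confidence bound, or an equivalent test against a shifted null, to show that the true deficit is smaller. Section 4 supplies neither. With no null value written, a p-value on the treatment coefficient is naturally read as a test of an odds ratio of 1.

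For two similar dyes the likely result is p≥0.05, and the plan does not say what that means. A reader could take it as non-inferiority and support replacing the standard-of-care dyes, although a large deficit had not been excluded. The opposite error is also possible: a small deficit in a large sample gives p<0.05 against the study dye although it may lie inside an acceptable margin.

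**Working it through.** The plan contains no sample size, power, expected success rate or margin, so it has no figure to reproduce. The check first lists what the criterion can conclude, then illustrates it. All rates and counts below are assumptions, and no propensity weights, covariates or imputation are included.

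**Possible outcomes under section 4**

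| Result | What it says about non-inferiority |
|---|---|
| p<0.05, study dye better | Implies it, at any margin |
| p≥0.05 | Nothing: a deficit may or may not be excluded |
| p<0.05, study dye worse | Nothing: the deficit may or may not exceed an acceptable margin |

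**Not significant, large deficit not excluded.** Take 34/40 (study) against 38/40 (comparator).
- Difference: 0.85 − 0.95 = −0.10. Pooled proportion: 72/80 = 0.90.
- Score test: SE = √(0.90 × 0.10 × 2/40) = 0.0671; z = −0.10/0.0671 = −1.49; p = 0.14.
- Logistic: coefficient = ln(34/6) − ln(38/2) = −1.210; SE = √(1/34 + 1/6 + 1/38 + 1/2) = 0.850; p = 0.15.
- Newcombe 95% CI, from Wilson limits 0.709 to 0.929 (study) and 0.835 to 0.986 (comparator):
  - lower = −0.10 − √[(0.85 − 0.709)² + (0.986 − 0.95)²] = −0.245
  - upper = −0.10 + √[(0.929 − 0.85)² + (0.95 − 0.835)²] = +0.040

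So p is well above 0.05, while a deficit of up to 24.5 points remains compatible with the data.

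**Significant, yet possibly acceptable.** Take 470/500 against 485/500.
- Difference: −0.03. Score p = 0.022; logistic p = 0.025.
- Wald SE = √(0.94 × 0.06/500 + 0.97 × 0.03/500) = 0.0131; 95% CI = −0.03 ± 1.96 × 0.0131, or −5.6 to −0.4 points (Newcombe −5.7 to −0.4).

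**How often.** Exact binomial enumeration of the two-sided pooled score test at 0.05, equal arms:

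| Eyes per arm | 20 | 30 | 40 | 60 | 100 |
|---|---|---|---|---|---|
| p≥0.05 when true success is 85% vs 95% | 85% | 74% | 65% | 54% | 32% |
| Study dye significantly better when both are 95% | 0.6% | 1.4% | 2.2% | 2.3% | 2.2% |

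The first row is how often a true 10-point deficit would go undeclared. The second is how often equal dyes would reach the one result that supports the hypothesis.

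**Pooling.** In 40,000 simulated null studies with 15 imputations, averaging p-values gave an error rate of 5.1% at 5% missing information and 5.7% at 30%. Averaging therefore barely changes the size of the test. Its relevance here is that averaged coefficients and p-values, as described, give no standard error from which to form a bound.

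**Side condition: an arm with no failures.** If exactly one arm has no failures, the logistic coefficient diverges. With q = (success rate)ⁿ, the chance is 2q(1 − q). At 95% success this is 46%, 22%, 9% and 1% for 20, 40, 60 and 100 per arm; at 90% it is 21%, 3%, 0.4% and about 0%. An unweighted fit of 40/40 against 39/40 stopped at a coefficient of 17.9 with a linearisation SE of 1.03. The coefficient depends on the stopping rule (other settings gave 19.9 and 28.9), but the SE stayed at 1.03, so the Wald p-value is spuriously tiny for a difference of one eye.

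**The case against.** **The software and the cited pooling method.** Each planned regression yields a standard error, and the source cited for the pooling may define a variance. That stands in part: the accurate statement is that the plan describes no pooled standard error, not that none could be obtained. It does not rescue the criterion, because without a margin even a correct interval leads to no decision.

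**Estimates on the proportion scale.** Section 2.3 refers to the proportion of success, and section 4 names an average treatment effect and reports percentages. So point estimates on that scale are foreseen. The bound and the rule are still missing.

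**Reliance on assumed values.** This is true of every figure above, and 500 per arm is a large sample for demonstration product used over eight months. The core finding follows from comparing sections 2.3 and 4 and does not depend on the figures.

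**Separate issues.** The zero-failure problem would arise under any hypothesis and matters mainly with success near 95% or above and small arms. The adjusted p-values may simply be covariate-adjusted. Both are secondary.

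**Retrospective data.** Success is taken from existing surgical reports, so the surgeons may already know how the dyes performed. Fixing a margin now therefore gives limited protection. This stands, and the fix allows for it.

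**Stakes.** The products are already CE-marked and the replacement decision is optional. That limits the harm, but the protocol chose this hypothesis and its analysis should answer it.

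**Conclusion.** The concern holds, and the plan must be changed. Followed exactly, section 4 can support the section 2.3 hypothesis only when the study dye is significantly better; every other result leaves the hypothesis unanswered. This is a wrong criterion for the stated hypothesis, not just missing detail. The main fault is the absent margin and confidence-bound rule; the pooling described adds to it by producing no standard error.

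Confidence in the mismatch is high because it rests on the text alone. Its practical size cannot be fixed from the documents. Under the assumed rates, a true 10-point deficit gives p≥0.05 in 32% to 85% of studies at 100 down to 20 eyes per arm, and equal dyes at 95% success reach the supporting result in at most 2.3%.

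**What to change.** Replace the primary criterion in section 4, separately for each dye pair:

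1. In each imputed dataset, estimate the standardised difference in success proportion (study minus comparator) from the weighted outcome model, with its standard error. This matches the scale named in section 2.3.
2. Pool estimates and variances over the 15 imputations by Rubin's rules instead of averaging p-values.
3. Conclude non-inferiority only if the lower limit of the pooled two-sided 95% CI lies above the margin (a negative difference). The sponsor should set and justify the margin before staining outcomes are extracted or compared, and record what was already known about them at that time.
4. State that p≥0.05 in a test of no difference is not evidence of non-inferiority.

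Two smaller additions: define what adjusted means for the p-values across the two dye pairs, and name a fallback if an arm has no failures, such as bias-reduced logistic regression with standardisation or a score-type interval.

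The cost is SAP text, a written margin justification and additional R code, with no new patients or data. The claim may become harder to make. With equal observed success of 95%, the Newcombe 95% CI reaches about 12 points either side at 38/40 per arm, 9 at 57/60, 7 at 95/100 and 5 at 190/200, before any loss from weighting or imputation.

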## 2.4 Time frame of the retrospective analysis

SEPTEMBER 2021 – APRIL 2022

## 3 Study Population / Eligibility Criteria

### 3.1 Inclusion criteria

Participants eligible for inclusion in this Study must meet **all** of the following criteria:

Adult patients who underwent for vitrectomy surgery where ILM and/or ERM removal is required:

- Macular holes (ILM staining)
- Macular pucker (ILM and ERM staining)
- Vitreomacular traction (ILM staining)

### 3.2 Exclusion criteria

Participants eligible for this Study must **not** meet any of the following criteria:

- Children aged <18 years
- Vitrectomy for other indication than mentioned in 3.1
- Patients that have concomitant eye disease that may influence the outcome of the surgery, e.g. terminal glaucoma
- Patients that did not comply to the postoperative examination visit 6-10 weeks after the surgery

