## STUDY SYNOPSIS

Title of clinical Study («Study»)	Efficacy and safety evaluation of MONOBLUE DUAL View and MONOBLUE ILM View vital stains during vitrectomy surgery
Protocol Short Title Acronym	NewBlueDyes
Sponsor name	University Hospitals Leuven (UZ Leuven)>
Principal Investigator	[name]. [name]
Contact Address PI	UZ Leuven, [name]
Contact Email PI	[contact]
Contact Phone PI	[name]
Other public database nbr	NA
Coordinating Investigator	NA
Medical devices	Monoblue Dual View Monoblue ILM View
Study rationale	Retrospective Data Collection
Primary objective	Efficacy: visualization of membranes stained based on binary subjective evaluation.
Secondary objective(s)	

• Efficacy: subjective assessment of surgical help provided by the product

• Safety:

○ Rate and severity of potential study-related products adverse events

○ Visual outcome at the last postoperative visit

Endpoints	Effectiveness Outcomes: Improvement in BCVA after 2 months as compared to preoperative BVCVA. Safety Outcomes: Safety will be assessed based on incidence and severity of investigational device-related adverse events.
Time frame of collecting data for retrospective analysis	SEPTEMBER 2021-APRIL 2022

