**Primary endpoint: Study product efficacy (success, defined as follows):**

From the surgical report, the following data will be extracted:

1. In case of surgery for macular hole or vitreomacular traction:

- A. Was the staining of the ILM satisfactory to initiate the peeling: yes / no
- B. Was the staining of the ILM satisfactory to create the ILM rhexis: yes / no
- C. Was it necessary to use another vital dye in order to obtain satisfactory staining: yes / no

Success is defined as answer “yes” to 1.A and/or 1.B

2. In case of surgery for macular pucker:

- A. Was the staining of the ERM satisfactory for its removal: yes / no
- B. In case the ILM was removed separately from the ERM:
  - i. Was the staining of the ILM satisfactory to initiate the peeling: yes / no
  - ii. Was the staining of the ILM satisfactory to create the ILM rhexis: yes / no
- C. Was MONOBLUE DUAL View repeatedly injected: yes / no
- D. Was it necessary to use another vital dye in order to remove the ERM: yes / no
- E. Was it necessary to use another vital dye in order to remove the ILM: yes / no

Success is defined as “yes” answer to 2.A and 2B.i or 2B.ii

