**Secondary endpoint: assessment of surgical safety**

The following endpoints will be used to determine surgical safety:

- Occurrence of adverse events during or after the surgery, whereby both treatment groups will be compared to the corresponding control groups (see above). Occurrence of adverse events will be collected over the duration of the study and up to week 6-10 postoperative, and will be assessed cumulatively.
- Visual outcome at the last postoperative visit, i.e. week 6-10 after the surgery

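### Missing the week 6-10 visit makes a patient ineligible for the whole study, although staining success is fully recorded at surgery; the visit should be required only for the week 6-10 endpoints

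*Combined protocol and SAP*

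**What the plan says.** Section 3.2 of the combined protocol and SAP lists four exclusion criteria that apply to the study as a whole. The fourth is "Patients that did not comply to the postoperative examination visit 6-10 weeks after the surgery". No section defines an analysis set by endpoint, gives a reason for this criterion, or asks how many patients it removes.

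The endpoints depend on that visit to different degrees:

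- **Staining success (primary).** Section 5.2 introduces the items with "From the surgical report, the following data will be extracted". Both success definitions, for macular hole or vitreomacular traction and for macular pucker, use only answers about what happened during surgery.
- **Adverse events (secondary).** Section 5.2 specifies "Occurrence of adverse events during or after the surgery, whereby both treatment groups will be compared to the corresponding control groups". Collection runs "up to week 6-10 postoperative, and will be assessed cumulatively". The intraoperative part is known at the end of surgery; the cumulative endpoint is not.
- **Vision (secondary).** Section 5.2 specifies "Visual outcome at the last postoperative visit, i.e. week 6-10 after the surgery". The synopsis gives "Improvement in BCVA after 2 months as compared to preoperative BVCVA". This endpoint needs the visit.

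On missing data, section 4 states: "In case of missing values, the underlying missingness process (MCAR, MAR or MNAR) will be investigated and 15 multiple imputations will be performed". Section 2.3 states the hypothesis as non-inferiority on staining success. Section 2.1 takes the controls from three earlier studies and does not describe their follow-up.

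**The concern.** The criterion selects patients on something that happens weeks after the primary endpoint has been recorded. Followed as written, it discards a valid surgical report whenever the patient did not return. For a non-inferiority comparison, fewer patients means a wider interval, however the test is carried out.

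The rate of adverse events is itself a secondary endpoint. If patients with an event return less often than others, or more often, the rate among attenders differs from the rate among all operated patients. Because the number of non-attenders per group is not requested, a reader of the results could not judge either effect.

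**Working it through.** The documents state no sample size, margin, success rate, event rate or missed-visit rate, so there is no figure of the plan to reproduce. Every input below is an assumption chosen to show a range.

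**1. Precision of the staining comparison.** If a share m of each group is excluded, the interval widens by 1/√(1−m) − 1. For scale, take 100 operated patients per group and 90% success in both. The 95% half-width of the difference is then 1.96 × √(2 × 0.9 × 0.1 / (100(1−m))).

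| Missed visit, m | Widening | Half-width (percentage points) |
|---|---|---|
| 0 | – | 8.32 |
| 5% | 2.6% | 8.53 |
| 10% | 5.4% | 8.77 |
| 20% | 11.8% | 9.30 |

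**2. Adverse-event rate of one product.** With true rate p, attendance a among patients with an event and b among the others, the rate among attenders is pa / (pa + (1−p)b). For p = 10%:

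| a | b | Observed rate |
|---|---|---|
| 70% | 95% | 0.070 / (0.070 + 0.855) = 7.6% |
| 80% | 95% | 0.080 / (0.080 + 0.855) = 8.6% |
| 95% | 95% | 10.0% |
| 95% | 80% | 0.095 / (0.095 + 0.720) = 11.7% |
| 95% | 70% | 0.095 / (0.095 + 0.630) = 13.1% |

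**3. Adverse events between groups.** The selection multiplies each group's odds by a/b. If a and b are the same in both groups, this factor cancels and the odds ratio is unchanged. Take true rates of 10% and 5%, with odds ratio (0.10/0.90) / (0.05/0.95) = 2.11:

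- (a, b) = (70%, 95%): 7.57% against 3.73%; odds ratio 2.11; difference 3.8 points instead of 5.
- (a, b) = (95%, 70%): 13.10% against 6.67%; odds ratio 2.11; difference 6.4 points instead of 5.

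**4. Retrieving non-attenders in one group only.** Let true success be 90% in both groups and success among non-attenders be s. Success among control attenders is then (0.90 − m·s)/(1−m). Comparing all study-product patients with control attenders gives a false difference:

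- m = 10%: s = 80% gives 91.11%, difference −1.1 points; s = 95% gives 89.44%, difference +0.6 points.
- m = 20%: s = 80% gives 92.50%, difference −2.5 points; s = 95% gives 88.75%, difference +1.25 points.

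Relaxing the rule therefore helps the main comparison only if it is relaxed in both groups.

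**5. Vision and imputation.** Section 4 says: "The next covariates were selected for the propensity score: age, gender, visual acuity of the affected eye", plus surgery type, and the outcome regressions include the same variables. If only the week 6-10 value is missing, and is missing at random given these variables, imputing it from them adds almost nothing to the adjusted regression in attenders. A gain would need further predictors, and the plan lists no intermediate postoperative vision. If missingness depends on the unseen vision itself, imputation under missing at random does not repair it.

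**The case against.** The strongest defence is that restricting a retrospective review to patients with complete follow-up is a recognised choice. It gives one denominator for all endpoints and full ascertainment of the cumulative adverse-event endpoint, and it avoids the asymmetry in step 4. The number excluded could be zero or negligible, and at 5-10% missed the assumed half-width grows by less than half a point. If the control records cannot be extended, the main comparison stays as planned.

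Most of this stands and limits the point. It justifies a complete-follow-up set for vision and cumulative adverse events. It does not justify discarding an intraoperative result that is already in the surgical report.

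Three stronger readings are tempting, and the documents do not support them:

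- *The staining comparison is biased.* Nothing in the documents links attendance at week 6-10 to the staining result. If the two are unrelated, only precision is lost.
- *The safety comparison is biased.* Attendance explained by age, gender, visual acuity or surgery type is addressed by the weighting and the adjusted regressions. Beyond that, the planned logistic comparison is distorted only if outcome-related attendance differs between study-product patients and controls. The follow-up of the three control studies is not described, so this can be neither asserted nor excluded.
- *The exclusion defeats an imputation that would have recovered the missing vision.* Step 5 shows that the imputation would add little.

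**Conclusion.** The point holds in a limited form and is worth correcting. The exclusion applies to the whole study by its wording. That it reaches every analysis is an inference from that wording, but no section keeps these patients for any endpoint.

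For staining success, the cost of any exclusion is precision: about 3%, 5% or 12% wider intervals at an assumed 5%, 10% or 20% missed. For a single product's adverse-event rate, an assumed true 10% could read between 7.6% and 13.1% across the attendance gaps tried. The odds ratio is unaffected when the attendance pattern is the same in both groups. All these figures rest on assumed inputs. The actual size and direction are unknown, and if few patients missed the visit the effect is small.

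**What to change.** Remove the visit from study eligibility and require it only for the week 6-10 endpoints.

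1. Analyse staining success, and report intraoperative adverse events, in all otherwise eligible operated patients. Apply the same rule to study-product and control groups, and show the attenders-only result beside it.
2. If control non-attenders cannot be retrieved, keep attenders-only as the main comparison and show the all-operated study-product result descriptively.
3. Report the number of non-attenders per group where it can be obtained.
4. For vision and cumulative postoperative adverse events, keep attenders with complete follow-up as the main analysis and report follow-up completeness by group. Imputing vision for non-attenders is at most a sensitivity analysis.

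The cost is a change to the eligibility and analysis-population wording, extraction of some further existing records, and different denominators by endpoint. The number of extra records, and whether they are available in the three control studies, is not stated. If they are not available for controls, the gain shrinks to a count of study-product non-attenders and a descriptive result.
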